## 5. AMENDMENTS AND UPDATES

Table 1 Amendments and updates

Number	Date	Section of study protocol	Amendment or update	Reason
1			None	

### 6. MILESTONES

Table 2 Study milestones

Milestones	Planned dates
Study protocol approved	15 June 2021
Clinical study report approved	
Operational information	Details
Budget holder(s), including cost-sharing	
Delivery model	
Planned data re-use	Not applicable
Approach towards patient centricity (e.g. engagement with patient groups related to study)	Not applicable
International coordinating investigator or executive steering committee	

## 7. RATIONALE AND BACKGROUND

The current COVID-19 pandemic constitutes a public health emergency unprecedented in the last century. From a small cluster of cases initially identified in 2019 in Wuhan, China, [2] the disease has spread around the globe. As of 4 April 2021, there have been more than 130 million confirmed cases and more than 2.8 million deaths globally. [3] SARS-CoV-2 (the viral agent that causes COVID-19) shares more than 79% of its sequence with SARS-CoV and 50% with the coronavirus responsible for Middle East respiratory syndrome (MERS-CoV). It is believed that evolution of the pandemic will further vary across countries, affected in part by different containment strategies ranging from extreme lockdown to relative inaction. As a result, there may be regional waves of the disease and pockets of deeply affected populations. Globally, governments have acknowledged that an effective vaccine against COVID-19 constitutes a major public health need and may be the only way to guarantee a safe and sustained exit strategy from human movement restrictions while avoiding escalating mortality rates across populations. Accelerated development of safe and effective vaccines and treatments are currently underway and focus on adults. Various vaccines against COVID-19 based on different technologies are now in clinical development around the world or have been recently authorized, with some being rolled in middle or high-income countries. Many of the vaccines display optimal immune

response and protection following 2 vaccinations, a prime and a boost vaccination separated by several weeks. As of 15 April 2021, over 29.4 million doses of the AstraZeneca vaccine had been administered in EU/EEA countries. 

A rare syndrome of thrombosis associated with low platelets has been reported in a few cases of recent exposure to COVID-19 vaccine. No causal association with COVID-19 vaccination has yet been established. The cases are unusual because, despite the thrombocytopenia, there is progressive thrombosis, primarily venous, with a high preponderance of cerebral venous sinus thrombosis. Some arterial thrombotic events have also been noted. Testing typically reveals low fibringen and very raised D-dimer levels above the level typically expected in venous thromboembolism. Antibodies to platelet factor 4 (PF4) have been identified, hence there are similarities to heparin-induced thrombocytopenia despite the absence of prior exposure to heparin treatment. This syndrome seems to be affecting patients of all ages and both genders; at present there is no clear signal of risk factors. However, there is little data regarding occurrence and risk factors of thromboembolism (TE) with thrombocytopenia (TCP) or its relationship with prior COVID-19 infection or COVID-19 vaccination. Several papers reported case series of thrombosis co-occurring with thrombocytopenia, also called thrombotic thrombocytopenia syndrome (TTS) or vaccine induced thrombotic thrombocytopenia. [5] These represented relatively small numbers of patients without clear characterization and without a comparison of the risk of events among non-vaccinated populations.

The Medicines and Healthcare products Regulatory Agency (MHRA) had requested for all cases of thrombosis or thrombocytopenia occurring within 28 days of coronavirus vaccine to be reported via the online yellow card system.  Up to and including 31 March 2021, the MHRA had received 79 United Kingdom (UK) reports of blood clotting cases alongside low levels of platelets following the use of the COVID-19 Vaccine AstraZeneca: 44 of the 79 cases were of cerebral venous sinus thrombosis (CVST) with thrombocytopenia 35 of the 79 cases were of thrombosis in other major veins with thrombocytopenia. These 79 cases occurred in 51 women and 28 men, aged from 18 to 79 years.  As of Apr 9, 5 cases of arterial thrombosis, 374 cases of deep vein thrombosis, 3 cases of jugular vein thrombosis, 7 cases of pelvic venous thrombosis, 1 subclavian vein thrombosis, 345 cases of thrombosis, one case of vena cava thrombosis, 21 cases of venous thrombosis and 22 cases of venous thrombosis limb, have being reported in the in the EudraVigilance database. 

Benefits are well-established while risks are very low, so it should continue to be used. In addition, recently drafted cases definitions being posed by the Brighton Collaboration currently suggest the following diagnoses are also of interest in defining probable cases: deep vein thrombosis (DVT), pulmonary embolism (PE), stroke, and myocardial infarction (MI).

The UK is one of the first countries that are introducing mass vaccination campaign for COVID-19 and has completed vaccinating the older half of the adult population starting from the oldest [10] Three age groups, by May 2021vaccien was being offered to people COVID-19 vaccines were licensed and are being used including the: Moderna, BioNTech/Pfizer, and Oxford/Astrazeneca vaccines. Vaccination with the BioNTech/Pfizer vaccine started in December 2020 and with the Oxford/AstraZeneca vaccine started in early January 2021. Also, The UK is uniquely placed to study this area because of its registrationbased primary care system (one patient registers with a single general practitioner), and a unique identifier National Health Service (NHS) number links primary care to secondary care data.

All general practices have had electronic links to their pathology systems since 2004, so that haematology tests (including platelet counts) and SARS-CoV-2 test results from any location nationally are recorded in the patient's computerised medical record (CMR). However, although SARS-CoV-2 testing is now readily available, that was not the case at the start of the pandemic.

However, prior to this there is a strong association with clinicians making a clinical diagnosis of COVID-19 and mortality. [9] Additionally, vaccination is well advanced maximising population wide vaccine exposure.

#### 8. **OBJECTIVE**

To evaluate an association between COVID-19 vaccine exposure and the outcome of thrombosis with thrombocytopenia syndrome (TTS).

#### 9. RESEARCH METHODS

#### 9.1 **Study design-General Aspects**

A case control study and a self-controlled case series (SCCS) will be designed and run, with a cohort analysis being considered in addition or as an alternative primary study design, pending feasibility assessment of the follow-up time available. The observation period will generally start on 02 December 2020 (approval date of the first COVID-19 vaccine) to the TTS event date or end of data availability, estimated mid May 2021 or another censoring event. There are several considerations to take when selecting the final study design/s. Firstly, some assumptions of the SCCS could be violated: 1) the occurrence of an event of interest must not alter the probability of subsequent exposure; and 2) the occurrence of the event of interest must not censor or affect the observation period. This is because in case of TTS occurring after the first dose of vaccine, the second dose could not be administered and/or because of a possible high CONFIDENTIAL AND PROPRIETARY

fatality rate associated with TTS. Observation period will be censored at the time of fatal events. In conclusion, the case-control design is likely to be more appropriate as the main analysis and SCCS is proposed as a sensitivity analysis for the non-fatal cases using the extended method for curtailed post-event exposure.

The matched case-control study will be conducted to determine the likelihood of those presenting with thrombotic thrombocytopenia (TTS) events within a risk window of 28 days of receiving COVID 19 vaccination. Patient who fulfils the definition of thrombotic thrombocytopenia based on a distribution of TTS spontaneously reported cases for COVID-19 vaccine AstraZeneca (sensitivity windows of 42 days as risk window for many immune-mediated vaccine safety events and as per EMA recommendation. We will conduct exploratory analyses on the dataset with the definitive analysis conducted on the national data held in the NHS Digital TRE, to identify people who presented with thrombotic, and thrombocytopenia events over a period (02 December 2020 to end of data availability, estimated mid May 2021) following COVID-19 vaccination. Electronic records of cases will be checked for any previous recorded history of conditions consisting of TTS; several wash-out periods will be considered including prior 90 days or prior for 12 months prior to the date of the index episode. Those without a previous record will be deemed to have experienced an incident diagnosis of a TTS on that date. Each incident case will be matched by date of TTS event,

Diagnosis dates of the cases will be considered the index dates for the controls. Records of both cases and controls will then be checked for the 28 days (sensitivity period of 42 days) before the index date for a previous ChAdOx1 and BNT162b2 or other COVID-19 vaccination.

For the self-controlled case series (SCCS), only individuals with a TTS event recorded during the defined study time are included in the analysis. Event and exposure history will be obtained from the linked dataset; events primarily extracted from hospital data. We will control for potential delaying of vaccination by the occurrence of an event by using the pre-vaccination risk period -7 to -1 days. Furthermore, since venous thromboembolism (VTE) is a likely indication for administration of a vitamin K antagonist (warfarin) or direct oral anticoagulants (DOAC), SCCS models with both vaccination and anticoagulation as exposures are potentially subject to event-dependent exposures, including recent infection. In this case we will perform a subgroup analysis of those with historical anticoagulation (defined by a prescription for

anticoagulation 90-days prior to the beginning of the study use versus those with no such history. We may also use this as a time varying covariate in our SCCS analysis). Another subgroup analysis will include prior exposure to COVID-19 infection. The observation period will commence 42 days before the first administration of a COVID vaccine in England, this results in the date 26th October 2020. The SCCS risk periods will be defined as days -7--1, 0-2, and 3-28 (our later analysis will extend to 42 days) where day 0 is the day of vaccination. This post vaccine period proposed is hypothesised to capture the time period within which most VTE events occur. A control period after 1st dose of 42 days will be considered. Given that most vaccinated in the UK were given the two-vaccine disease with about 3-month (90 days) time interval, we will check, but will not expect a high probability of overlapping of risk period after 2nd dose.

For the retrospective cohort design, the incidence of TTS after receiving COVID-19 vaccine will be estimated and we will compare this incidence with that occurring in an unvaccinated comparator group. A cohort of concurrent matched subjects will be selected. The comparison cohort will comprise subjects who have not yet received any COVID-19 vaccine.

[figure not shown]
. The rationale for matching on calendar date is to control for the temporal variation in the SARS-CoV-2 circulation (COVID-19 infection may affect risk of some AESIs) and expected changes in vaccinee characteristics over time. Propensity scores (PS) will be used to address confounding, balancing multiple covariates such as prior COVID-19 infection, comorbidities, and markers of health care utilisation between vaccinated and unvaccinated cohorts. Relative risk will be the main measure of effect, which will be estimated using incidence rate ratios (IRRs) or hazard ratios (HRs), depending on the analysis and outcome. The proposal to use concurrent, rather than historical, comparator (unvaccinated) subjects is because they are at risk for COVID-19, and COVID-19 may function as an important covariable in the analyses of several of the safety endpoints. The potential challenge with this approach is that during the pandemic, unvaccinated subjects in the comparator group may themselves become vaccinated over time. The rationale for not selecting historical pre-pandemic subjects for primary comparison pertains to concerns over non-comparability. The background rate of TTS may have changed during the pandemic because of COVID-19 or because of less intensive ascertainment due to access issues or health-seeking behaviours.

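### The SCCS post-dose control period has no stated days, so days 29-42 can become reference time in the 28-day analysis although the protocol elsewhere treats them as risk time

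*Protocol*

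**What the plan says.** Section 9.1 sets a pre-vaccination window of days -7 to -1 and then the intervals "0-2, and 3-28 (our later analysis will extend to 42 days) where day 0 is the day of vaccination". It then says "A control period after 1st dose of 42 days will be considered", with no start day, no end day and no statement of which analysis the sentence applies to. The SCCS observation period is given its own start: "The observation period will commence 42 days before the first administration of a COVID vaccine in England, this results in the date 26th October 2020". Time well before vaccination is therefore available as reference time. On the second dose the section refers to an "about 3-month (90 days) time interval, we will check, but will not expect a high probability of overlapping of risk period after 2nd dose".

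Other sections use 42 days as risk time. The case-control part of 9.1 takes 28 days with 42 as the sensitivity window. The study-size note in 9.4 assumes a 42-day risk interval per dose. Section 9.6.4 estimates odds ratios for a 42-day risk period. Section 9.6.3 fits the SCCS by conditional Poisson regression. Section 9.8 says other SCCS risk intervals may be explored, and 9.12 names possible attenuation from uncertain risk periods.

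**The concern.** In an SCCS every observed day is either in a listed risk interval or in the baseline. A model that lists only -7 to -1, 0-2 and 3-28 therefore puts days 29-42 in the baseline unless the plan removes them, and nothing in the protocol does. Those 14 days are the ones that the extended analysis would count as risk.

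If vaccine-related events occur in days 29-42, they raise the baseline rate and pull the days 3-28 RI towards 1. In a safety study that error runs towards missing harm. In addition, moving from the 28-day to the 42-day analysis changes the risk window and the baseline together, so a difference between the two results is harder to interpret.

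**Working it through.** **Readings of the 42-day control period**

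1. The 42 days straight after dose 1. Days 0-28 are already risk time, so the only post-dose control days are 29-42 (14 days). The extended analysis then has no post-dose control time and relies on pre-vaccination time.
2. 42 days following the 28-day risk period, that is days 29-70. Of these, 14 of 42 (33%) are risk days in the extended analysis.
3. Control time that begins once 42 days have passed, from day 43. No control day is an extended-risk day. This protects the 28-day analysis only if days 29-42 are also excluded or coded separately, which the protocol does not state.

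**Inputs.** The protocol gives no bias or precision figure on this point, so there is none to reproduce. The SCCS observation start (26 October 2020), the -7 to -1 window and the risk intervals come from 9.1. Assumptions:
- dose 1 on 15 February 2021 for every case;
- observation to 15 May 2021, as the estimated mid-May end of data;
- one dose and a constant baseline rate;
- true RI R = 4 in days 3-28, and r in days 29-42. The protocol gives neither R nor r.

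**Day counts**
- 26 October to 15 February is 112 days; less the 7 pre-exposure days, 105 control days before the dose.
- Days 29-42 are 14 days, and days 43-70 are 28 days.
- 15 February to 15 May is 89 days; 89 - 42 = 47 days after day 42.

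**Formula.** With C control days outside days 29-42, and the 14 days counted as control, the baseline is inflated by (C + 14r)/(C + 14). The large-sample estimate for days 3-28 is then 4 × (C + 14)/(C + 14r).

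| Post-dose control time | C | r = 1 | r = 2 | r = 3 | r = 4 |
|---|---|---|---|---|---|
| Days 29-42 | 105 | 4.00 | 3.58 | 3.24 | 2.96 |
| Days 29-70 | 105 + 28 = 133 | 4.00 | 3.65 | 3.36 | 3.11 |
| Day 29 to mid May | 105 + 47 = 152 | 4.00 | 3.69 | 3.42 | 3.19 |
| From day 43, days 29-42 kept out | any | 4.00 | 4.00 | 4.00 | 4.00 |

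Example, first row, r = 2: (105 + 28)/119 = 1.118, and 4/1.118 = 3.58. The third row is the default model, in which all unlisted time is baseline. Its last 7 days (83-89) would be the pre-exposure window of a second dose at day 90. Without them C = 145, and the results are 4 × 159/173 = 3.68 at r = 2 and 4 × 159/201 = 3.16 at r = 4, almost unchanged.

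**Comparing the two analyses.** If days 3-42 are fitted as one interval against a clean baseline, the RI is (26 × 4 + 14r)/40. That is 2.95 at r = 1, 3.30 at r = 2 and 4.00 at r = 4. The 28-day analysis gives 4.00 at r = 1 and 2.96 to 3.19 at r = 4. The gap between the analyses therefore mixes the wider window with the altered baseline.

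**The case against.** The strongest reply is that the protocol never says days 29-42 are control time. Reading 3 is open, and on it the control period may already start where it should. This stands against any claim that the control window does overlap the risk window. It does not remove the need to state the days, because even on reading 3 the status of days 29-42 in the 28-day model is unstated.

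Four stronger inferences are tempting, and the document does not support them:

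- **Overlap within one model.** The 28-day and 42-day windows belong to separate analyses. Within either fitted model a day is risk or reference, never both.
- **Attenuation as a fact.** It needs a raised incidence in days 29-42, for which the protocol gives no figure. At r = 1 there is none, and r = 4 is the extreme case in which late risk equals early risk.
- **Much larger losses, from treating the 42 days as the only reference time.** The SCCS observation start in October 2020 supplies pre-vaccination reference time.
- **Weak grounds for stopping at day 28.** A reader might infer that late cases are under-represented because the UK regulator asked for "thrombocytopenia occurring within 28 days of coronavirus vaccine to be reported via the online yellow card system". The protocol does not say that its 28-day window was derived from those reports. Section 7 also cites European reports with no 28-day limit stated, and for the SCCS section 9.1 gives a different rationale, based on when most venous events are expected.

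It can also be said that interval coding belongs in the SAP, that 9.8 and 9.12 show awareness of the issue, and that separate RIs may already be intended because all risk intervals are to be reported. But the protocol itself fixes the risk intervals and a control length and leaves the two unreconciled. Section 9.8 only considers exploring other intervals, and 9.12 names the bias without preventing it.

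**Conclusion.** The point holds as an incomplete definition with a conditional bias. The control days are not stated. On two of three readings, and by default in a model with only the listed risk periods, days 29-42 are baseline in the 28-day analysis while being risk time in the extended one.

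If and only if incidence is raised in days 29-42, the days 3-28 RI is understated. Under the working assumptions the loss is at most about a quarter (4 to 2.96) and about a tenth at r = 2 (4 to 3.58). These sizes depend on the assumed RIs, the single vaccination date and the amount of pre-dose time, and are illustrative. The differing baselines make the 28-day and 42-day results harder to compare, but not uninformative.

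The weight is moderate. Section 9.1 proposes the SCCS as a sensitivity analysis for non-fatal cases, although the abstract lists it as one of two primary designs. The change is worth making because it is cheap and removes the possible bias on every reading.

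**What to change.** In section 9.1, replace the control-period sentence with explicit days that apply to all SCCS models:

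- Code days 29-42 as a separate interval with its own RI, in the 28-day analysis as well as the extended one.
- Start post-dose control time at day 43.
- End it before the -7 to -1 window of dose 2, using each person's actual dose 2 date. At a 90-day interval that window is days 83-89, so control runs over days 43-82 (40 days). A full 42 days (43-84) would run 2 days into the window.
- State that pre-vaccination time outside the -7 to -1 window is also reference time.

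Both analyses then share one baseline, and the days 29-42 estimate shows directly whether the 28-day window is adequate. A combined days 3-42 RI can still be reported against the same baseline.

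The cost is one extra model term, a short change of text and 14 fewer control days per person. In the example, control time falls from 166 to 152 days (14/166, about 8%), or from 119 to 105 (14/119, about 12%) if control would otherwise have ended at day 42. The loss of precision is small.

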## 9.2 Variables and Data Sources

**Table 3** lists the groupings of variables available for this study by data source. Exposure data are described in the Vaccinations category. Outcome data are described in the primary care, secondary care use and mortality (as recorded in primary care data). The rest of the categories contain data on potential confounding variables and effect modifiers.

Table 3 Data items/variables and data sources

Data category	Data item	Data source
	In addition, we will look to identify:	

## 9.2.1 Exposure of interest

First dose o accines recorded in RCGP RSC. Uncertain vaccine type after 1/1/2021 when both vaccines were available, will be excluded. Uncertain vaccines administered during December will be assigned to the People will be excluded with a second dose within the follow-up window.

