#### Methods:

**Study design:** Two primary study designs will be considered, a case control study and a self-controlled case series (SCCS). A cohort analysis will be considered, in addition or as an alternative to either of the primary study designs, pending feasibility assessment of the follow-up time.

**Data Source(s):** We will conduct retrospective studies using linked secondary databases in England. Data for the definitive study accessed through the NHS Digital Trusted Research Environment (TRE), providing national data coverage. Primary care data will be linked with vaccination, hospitalization, COVID-19 test results, mortality data. Initial exploratory analyses will be conducted using the

Study Population: Subjects of interest are people who

However, we will required access to data from patients, in the integrated health records of at the start of each study period. We need to make comparisons with unvaccinated, and our analysis needs information about levels of infection across the whole population.

Variables: Demographic, socioeconomic descriptors, clinical diagnosis, vaccines, potential confounders, thrombotic phenomena, COVID-19 infection, and other characteristics as applicable.

**Statistical Analysis:** Counts of cases will be reported by will start on December 02, 2020, when the COVID-19 vaccine was first approved in the UK and will end approximately by end in May or at the end of data availability.

For the case-control design, all cases of TTS will be matched with control using risk-set matching. A case or matched control will be considered exposed if a COVID-19 vaccination will be within risk interval prior to the diagnosis date of the matched case.

For the SCCS, estimates of relative incidence (RI), in all risk intervals will be reported. RI will also be reported in the Joint Committee for Vaccinations and Immunisation's (JCVI's) vaccination risk and age groups. Seasonal effects are not deemed relevant. Cumulative hazard plots for gap times will be provided, and we will investigate if the inclusion of pre-exposure risk periods affects incidence of adverse events of interest associated with vaccination using a sequence of values and exploring whether RI is sensitive to the choice of pre-exposure period.

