#### 9.6.4 Matched case-control

For matched case-control analysis, the sampled risk sets will be represented matched strata, which will be included in conditional logistic regression models to estimate odds ratios (OR) for the risk of the event in the 42-day risk period.

. Confounding may to be due to time varying confounders that will be much harder to adjust for than in our case-control study. We will also have confounding due to the differential availability of the vaccines, their storage requirements and intervals between doses (initially short and applied mainly to one brand) and then lengthened. We may be able to adjust for those that are measured and complete;

as well as recognising others may be unmeasured (such as occupation). We will stratify exposure by dose as an exploratory analysis.

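### Section 9.2.1 excludes uncertain-type vaccinations after 1/1/2021 without saying whether the dose or the person is dropped: one reading attenuates the OR, the other needlessly loses exposed cases

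*Protocol*

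**What the plan says.** Section 9.2.1 of the protocol sets the rule: "Uncertain vaccine type after 1/1/2021 when both vaccines were available, will be excluded". The sentence is complete in the public text, but its subject is the vaccine type, not a dose or a person. Two neighbouring rules differ. For second doses the excluded unit is named: "People will be excluded with a second dose within the follow-up window". For the period before a second product was available, uncertain doses are kept: "Uncertain vaccines administered during December will be assigned to the" is followed by a gap, so the product they are assigned to cannot be read.

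Elsewhere exposure does not depend on product. The abstract says of the case-control design: "A case or matched control will be considered exposed if a COVID-19 vaccination will be within risk interval prior to the diagnosis date". Section 9.1 gives the look-back, "Records of both cases and controls will then be checked for the 28 days (sensitivity period of 42 days) before the index date", and lists the two named vaccines together with any other COVID-19 vaccination. The objective in section 8 concerns COVID-19 vaccine exposure in general. For the cohort design, section 9.1 states: "The comparison cohort will comprise subjects who have not yet received any COVID-19 vaccine".

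The case-control analysis in section 9.6.4 uses "conditional logistic regression models to estimate odds ratios (OR) for the risk of the event in the 42-day risk period", with the sampled risk sets as strata.

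**The concern.** A person known to have been vaccinated in the risk interval, with the product unrecorded, is exposed under the abstract and sections 8 and 9.1, and cannot be an unvaccinated comparator. Section 9.2.1 nevertheless excludes that vaccination, and the visible text does not reconcile the two. An analyst can follow the rule in two ways.

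- **Dose dropped.** The record is deleted and the person stays. With no other dose on file, the person looks unvaccinated and enters the unexposed reference or the comparator cohort. In the self-controlled case series, the days after that dose would count as control time.
- **Person dropped.** The person leaves the analysis. If that person is a case, the whole matched set goes too, for an outcome that the abstract describes as very rare.

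The first hides part of any true effect, which is the unsafe direction in a vaccine-safety study. The second discards information because of a variable that an any-vaccine estimate does not use.

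**Working it through.** The documents state no figure for this point. The share of uncertain type is not given and the cells of the study-size table are not legible, so the inputs below are assumptions shown as ranges.

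**Inputs.** R = true odds ratio, illustrated at 5. p = proportion of controls exposed in the risk interval, 10% to 50%. u = share of exposed people whose product is uncertain, 1% to 10%. All three are assumed.

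**Dose dropped, same u in cases and controls.** Observed exposed controls are p(1−u) and observed unexposed controls are (1−p)+up. Cases are in the ratio Rp(1−u) to (1−p)+upR. Hence

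OR_obs = R[(1−p)+up] / [(1−p)+upR].

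In counts, with p = 30% and u = 10%: 100 controls are truly 30 exposed and 70 unexposed, and are recorded as 27 and 73. Cases scaled to 70 unexposed have 150 exposed, and are recorded as 135 and 85. The observed OR is (135 × 73)/(85 × 27) = 9855/2295 = 4.29.

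| Controls exposed | u = 1% | u = 2% | u = 5% | u = 10% |
|---|---|---|---|---|
| 10% | 4.98 | 4.96 | 4.89 | 4.79 |
| 30% | 4.92 | 4.84 | 4.61 | 4.29 |
| 50% | 4.81 | 4.64 | 4.20 | 3.67 |

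At R = 1 the numerator and denominator are equal and there is no bias. At u = 1% and p = 30% the fall is (5 − 4.92)/5, or about 1.7%.

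**Person dropped.** Exposed cases are multiplied by (1−u_case) and exposed controls by (1−u_control), while the unexposed cells do not change:

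OR_obs = R(1−u_case)/(1−u_control).

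With equal u the factor is 1. In the same counts, (135 × 70)/(70 × 27) = 5.00. A simulation of 200,000 matched sets (1:4, an assumed ratio) analysed by conditional logistic regression agrees: at u = 20%, true ORs of 2, 5 and 10 are estimated as 1.99, 4.99 and 9.90.

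Bias under this reading needs a further condition:

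- *u differs by case status.* With 5% in cases and 10% in controls, the factor is 0.95/0.90 = 1.06. Reversed, it is 0.90/0.95 = 0.95.
- *Doses after the index date trigger removal.* Suppose u = 5%, 80% of unexposed controls are vaccinated later, and 0% to 40% of unexposed cases are. The factor is then (1 − 0.8 × 0.05)/(1 − 0 × 0.05) = 0.96 to (1 − 0.8 × 0.05)/(1 − 0.4 × 0.05) = 0.98.
- *u differs by product and products are pooled.* Suppose product ORs are 5 and 1, with 40% and 60% of exposed controls. The pooled OR is 0.4 × 5 + 0.6 × 1 = 2.60. With u of 10% and 2% it becomes (5 × 0.36 + 0.588)/(0.36 + 0.588) = 2.52. The product-specific ORs do not change.

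The documents establish none of these conditions.

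**The case against.** The best defence is that the protocol, read as a whole, points to dropping the person. If any vaccination is exposure and the comparator must be wholly unvaccinated, nobody with an uncertain-type dose can properly sit in the reference, and dropping the person has no inherent bias. This has force, but it relies on the reader to resolve what section 9.2.1 leaves open. The contrast with the second-dose rule, which does name people, pulls the other way.

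This is also a post-authorisation study for one product, and section 9.1 names two vaccines. Excluding unknown product is conventional for brand-specific exposure. That stands for brand-specific estimates. It does not justify the exclusion in an any-vaccine estimate, which is how the objective is worded.

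Section 9.2.1 has gaps, and section 9.11 on missing data shows no text although the checklist in Appendix B says the methods are described there. Relevant handling may have been removed from the public copy, and nothing missing is counted here. The excluding sentence itself is intact.

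Section 9.13 claims near-complete assessment of exposure. If that extends to product, u is small and so is the attenuation.

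A reader might infer that the OR is biased whichever way the rule is read, on the ground that product is better recorded in TTS cases because section 7 reports that the regulator asked for such cases to be reported. The documents do not support this. Removal by exposure alone cancels in an odds ratio. The reporting request says nothing about how completely product is recorded, and section 9.2.1 takes exposure from primary care records, not from those reports.

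**Conclusion.** The point holds as a conflict between section 9.2.1 and the protocol's own definition of exposure, with an unstated unit of exclusion.

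If the dose is dropped, any true effect is attenuated. The loss is negligible to modest at a 1% uncertain share and material at 10%, where a true OR of 5 could be seen as low as 3.67. These sizes rest on assumed values of u, p and R. The 3.67 needs both a 10% share and half of controls vaccinated within the risk interval.

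If the person is dropped, the certain cost is precision: exposed cases and their matched sets are lost. Bias is possible only under the further conditions worked through above, and its direction depends on which of them applies. It should not be presented as a consequence of the rule itself.

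**What to change.** Replace the exclusion in section 9.2.1 with a rule based only on doses given on or before the index date:

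- In any-vaccine estimates, count a person with an uncertain-type dose in the risk interval as exposed.
- In brand-specific models, keep such people as a separate level, vaccinated with type uncertain.
- In every design, keep them out of the unexposed reference and the unvaccinated comparator.
- Report the share of uncertain type separately for cases and controls, so that the assumption of equal shares can be checked.
- As a sensitivity analysis of the brand-specific estimates, assign all of them first to one product and then to the other.

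The protocol already keeps uncertain December doses by assigning them, so retaining such records is not new to it. That rule is a single assignment, however, so the two bounding runs would be an addition. The cost is revised wording, one extra exposure level and a little more analysis. No new data are needed.
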